#### 9.2.1 EQ-5D

The EuroQol-5D (EQ-5D) is a standardized instrument for use as a measure of health outcome. The EQ-5D will provide data for use in economic models and analyses including developing health utilities or quality adjusted life-years (QALYs).

The 5-level version of the EQ-5D (EQ-5D-5L) ([EuroQol Group 1990](#); [Herdman 2011](#)) will be used to assess treatment effects on perceived health status and to generate utility data for health economic evaluations. The EQ-5D-5L is a generic multi-attribute health-state classification system by which health is described in 5 dimensions: mobility, self-care, usual activities, pain/discomfort, and anxiety/depression. Each dimension is evaluated using 5 response levels: no problems, slight problems, moderate problems, severe problems, and extreme problems.

Responses to these 5 dimensions are converted into 1 of 3,125 unique EQ-5D health state descriptions, which range between no problems on all 5 dimensions (11111) to extreme problems on all 5 dimensions (55555). Using appropriate country-specific value weighting algorithms, a respondent's self-described health state can be converted into a utility index representing the

societal desirability of his or her own health. In addition, the EQ-5D includes a visual analogue scale (VAS) allowing a respondent to rate his/her health on a scale ranging from 0-100 with 0 being the worst health state imaginable and 100 being the best health state imaginable.

The EQ-5D-5L uses a recall period of today.

### 9.2.2 EORTC QLQ-C30 and EORTC QLQ-H&N35

The EORTC QLQ-C30 ([Aronson 1993](#)) is the most commonly used quality of life instrument in oncology trials. The EORTC QLQ-C30 is composed of multi-item scales and single item measures. These include 5 functional scales (physical, role, emotional, cognitive, and social), 3 symptom scales (fatigue, nausea/vomiting, and pain), a global health status/HRQoL scale, and 6 single items (dyspnea, insomnia, appetite loss, constipation, diarrhea, and financial difficulties). Each of the multi-item scales includes a different set of items – no item occurs in more than one scale.

The EORTC QLQ-H&N35 is in use worldwide as one of the standard instruments for measuring quality of life in head and neck cancer patients ([Mehanna 2006](#); [Tschiesner 2008](#)) and consists of 7 multi-item scales measuring pain in the mouth, problems with swallowing, senses, speech, social eating, social contact, and sexuality, and 11 single-item scales assessing problems with teeth, mouth opening, dry mouth, sticky saliva, coughing, feeling ill, use of analgesics, use of nutritional supplements, use of feeding tube, weight gain, and weight loss ([Bjordal 1999](#); [Bjordal 1994](#)). The EORTC QLQ-C30 and EORTC QLQ-H&N35 are psychometrically and clinically validated instruments appropriate for assessing quality of life in patients with head and neck cancer. These instruments were used in the EXTREME registration trial (NCT00122460) comparing platin-5-fluorouracil alone versus combined with cetuximab as first-line treatment in recurrent or metastatic HNSCC, which led to the FDA approval of cetuximab monotherapy in patients with recurrent or metastatic HNSCC refractory to cisplatin ([Bjordal 2000](#); [Chera 2014](#)). They were also used in the Phase 3 trial of patients with locoregionally advanced head and neck cancer receiving radiotherapy alone or radiotherapy plus cetuximab ([Tschiesner 2008](#)).

For the global health status/quality of life and function scales, a higher value indicates a better level of function; for symptom scales and items, a higher value indicates increased severity of symptoms. Prior literature indicates that head and neck pain and the ability to swallow are clinically relevant symptom measures in the recurrent or metastatic HNSCC population ([Bjordal 2000](#); [Chera 2014](#); [Mesia 2010](#); [Machiels 2014](#)). Thus, time to deterioration in the pain and swallowing multi-item scales of the EORTC QLQ-H&N35, in addition to time to deterioration and mean change from baseline in global health status/quality of life scale of the EORTC QLQ-C30, will be evaluated as secondary objectives.

Both the EORTC QLQ-C30 and EORTC QLQ-H&N35 use a recall period of the past week.

## 10.0 ASSESSMENT OF SAFETY

### 10.1 AE Definition and Assessment

An AE is defined as any untoward medical occurrence in a clinical investigation patient administered a pharmaceutical product, at any dose, not necessarily related to the treatment.

An AE can therefore be any unfavorable and unintended sign, symptom, or disease temporally associated with the use of a medicinal product, whether or not considered related to the medicinal product. An AE can also arise from any use of the drug and from any route of administration, formulation, dose, or overdose. This definition includes intercurrent illnesses or injuries, and exacerbation of pre-existing conditions. Clinical laboratory, vital sign, or physical examination abnormalities will only be reported as AEs if they are deemed clinically significant by the Investigator (eg, associated with signs and symptoms, require treatment, or require follow-up).

Adverse events, SAEs, and other reportable safety events will be reported by the patient (or, when appropriate, by a caregiver, surrogate, or the patient's legally authorized representative). The investigator and any designees are responsible for detecting, documenting, and reporting events that meet the definition of an AE or SAE as well as other reportable safety events. The Investigator should attempt to establish a diagnosis of the event based on signs, symptoms, and/or other clinical information. In such cases, the diagnosis will be documented as the AE and/or SAE and not the individual signs/symptoms.

Care will be taken not to introduce bias when detecting AEs and/or SAEs and other reportable safety events. Open-ended and nonleading verbal questioning of the patient is the preferred method to inquire about AE occurrence.

For all reports of overdose (whether accidental or intentional) with an associated AE, the AE term should reflect the clinical symptoms or abnormal test result. An overdose without any associated clinical symptoms or abnormal laboratory results is reported using the terminology "accidental or intentional overdose without adverse effect."

An AE does not include:

- A medical or surgical procedure (eg, surgery, endoscopy, tooth extraction, or transfusion); an AE is the underlying condition that leads to the procedure.
- Pre-existing diseases or conditions present or detected before start of study drug(s) administration that do not worsen or increase in severity or frequency after the administration of study drug(s).
- Situations where an untoward medical occurrence has not occurred (eg, hospitalization for elective surgery for a condition that has not worsened on study, social and/or convenience admissions to grant families a respite in caring for a patient).

- Anticipated day-to-day fluctuations of pre-existing disease(s) or condition(s) present or detected at the start of the study that do not worsen.
- Surgical procedure(s) planned prior to informed consent to treat a pre-existing condition that has not worsened.

## 10.2 Monitoring AEs

All AEs will be assessed by the Investigator and recorded, including but not limited to, the following: the event term, the date of onset and resolution, seriousness, severity, relationship to study drug(s), outcome, treatment of the event, and action taken with the study drug(s). AEs will be reported starting immediately after the patient has been administered the first dose of study drug(s) until 30 days after the last dose of study drug(s). For serious AEs (SAEs), additional reporting requirements also apply (see Section 10.7).

An event occurring after the patient has provided informed consent, but before the first dose of study treatment or confirmed screen failure, will be collected as medical history unless the event is either new and attributed to protocol-mandated procedures by the Investigator or there is a significant change in the rate of occurrence or an increase in the severity of the pre-existing condition which is judged to be clinically important and attributed to the protocol-mandated procedures by the Investigator. Under the latter 2 circumstances, the event will be considered an AE and will be captured as such.

- Example 1: Thrombophlebitis associated with a blood draw for assessments required prior to dosing per protocol is an event that is related to protocol-mandated procedures. In this scenario, the event of “thrombophlebitis” will be captured as an AE, and it will be documented as being “unrelated” to study drug(s), as applicable.
- Example 2: An ankle sprain following an unexpected fall from a flight of stairs while at home, after the patient has provided informed consent, but before the first dose of study drug(s), is clearly unrelated to any protocol-mandated procedures and would therefore be captured as medical history.

## 10.3 Grading of AEs

The severity of an event and the seriousness are not to be considered synonymous. The severity is grading the intensity of an event. The seriousness of event is based on the patient/event outcome or action criteria. All AEs will be assessed for severity using the National Cancer Institute Common Terminology Criteria for Adverse Events (NCI-CTCAE) version 5.0 guidelines. If a particular AE is not listed in the NCI-CTCAE, the following criteria will be used:

- Grade 1 = Mild (event results in mild or transient discomfort, not requiring or needing only minimal intervention or treatment; does not limit or interfere with daily activities [eg, insomnia, mild headache]).

- Grade 2 = Moderate (event is sufficiently discomforting so as to limit or interfere with daily activities; may require interventional treatment [eg, fever requiring antipyretic medication]).
- Grade 3 = Severe (event results in significant symptoms that prevent normal daily activities; may require hospitalization or invasive intervention).
- Grade 4 = Life threatening or disabling.
- Grade 5 = Death.

AEs will be reported with an individual start and stop date for each level of severity.

#### 10.4 Causality Relationship of AEs

In combination therapy, it is often not possible to distinguish causal association of treatment-emergent AEs with specific study drug especially when both drugs contribute to activation of the body's immune mechanism. However, medical judgment is to be used to assess AEs based on unique immune activation pathways of each drug, time to onset from therapy drug administration, and known safety profiles of checkpoint inhibitors and IL-2 therapy. A general guidance on causal association assessment is provided below. In absence of clear evidence on causal association, relatedness is suggested to be assigned to both drugs after ruling out alternative etiologies based on medical history, concurrent illness, concomitant medications, etc. The relationship of each AE to each study drug (bempegaldesleukin or pembrolizumab) as applicable will be evaluated by the Investigator using the following definitions:

- Not related: An AE that does not follow a reasonable temporal sequence from administration of study drug(s), and/or that can be reasonably explained by other factors such as the patient's medical history, pre-existing medical condition, underlying disease, concurrent illness, or concomitant medications/therapies.
- Related: There is a reasonable possibility that the AE is caused by the study drug(s). A plausible temporal sequence exists between the time of administration of the study drug(s) and the development of the AE. The AE cannot be reasonably explained by the known characteristics of the patient's clinical state or other concomitant therapies or interventions administered to the patient.

#### 10.5 AE Reporting and Follow-up

After initiation of study drug treatment, all AEs (both nonserious and serious AEs) will be reported from the time of first study drug(s) administration until 30 days after the last dose of all study drug(s) (ie, (Follow-Up Visit 1) and only SAEs until 90 days after the last dose of all study drugs (ie, Follow-Up Visit 2). Additionally, AEs related to protocol-mandated procedures occurring between the signing of consent and first dose of study drug will be reported (see Section 10.2). Progression of the head and neck cancer under study and death related to the progression of this cancer will not be reported (see Section 10.9).

All initial and follow-up AEs, SAEs, and other reportable safety events will be recorded and reported to the Sponsor or designee within the time frames indicated in [Table 11](#).

All ongoing AEs will be followed until resolution, the patient is lost to follow-up (as defined in [Section 6.2.7](#)), patient death, or until the Follow-Up Visit 2. If the AE has not completely resolved by the last Follow-Up Visit, the final outcome of these ongoing AEs will be captured as “Not Recovered/Not Resolved” or “Recovering/Resolving”, whichever is applicable.

For specific instructions on identifying and reporting SAEs, see [Sections 10.6](#) and [10.7](#).

**Table 11: Reporting Time Periods and Time Frames for Adverse Events and Other Reportable Safety Events**

Type of Event	Reporting Time Period: Consent to Randomization/ Allocation	Reporting Time Period: Randomization/ Allocation through Protocol-specified Follow-up Period a	Reporting Time Period: After the Protocol-specified Follow- up Period	Time Frame to Report Event and Follow-up Information to Sponsor
NSAE	Report if: - due to protocol-specified intervention - causes exclusion	Report all	Not required	Per data entry guidelines
SAE including Cancer b and Overdose	Report if: - due to protocol-specified intervention - causes exclusion	Report all	Report if: - drug/vaccine related. (Follow ongoing to outcome)	Within 24 hours of learning of event
Pregnancy/ Lactation Exposure	Report if: - patient has been exposed to any protocol-specified intervention (eg, procedure, washout)  Exception: A positive pregnancy test at the time of initial screening is not a reportable event.	Report all	Previously reported – Follow to completion/termination; report outcome	Within 24 hours of learning of event
ECI (require regulatory reporting)	Report if: - due to intervention - causes exclusion	Report - potential DILI - require regulatory reporting	Not required	Within 24 hours of learning of event
ECI (do not require regulatory reporting)	Report if: - due to intervention - causes exclusion	Report - non-DILI ECIs and those not requiring regulatory reporting	Not required	Within 5 calendar days of learning of event
AESI (require regulatory reporting)	Report if: - due to intervention - causes exclusion	Report all	Not required	Within 24 hours of learning of event

Abbreviations: AESI = adverse event of special interest; DILI = drug-induced liver injury; ECI = Event of Clinical Interest; NSAE = nonserious adverse event; SAE = serious adverse event.

- a. Follow-up period includes:
  - Follow-Up Visit 1: reported until 30 days after the last dose of all study drug(s) and
  - Follow-Up Visit 2: reported only for SAEs until 90 days after the last dose of all study drug(s).
- b. A new cancer that is not a condition of the study indication.

## 10.6 Serious AE Definition

An SAE is defined as any untoward medical occurrence that at any dose:

- Results in death.  
Note: Death is an outcome of an AE and not an AE in itself. All events leading to death, regardless of relationship to study drugs, that occur during the protocol-specified reporting period, must be reported with the exception of deaths attributed to disease progression (refer to Section 10.9).
- Is life threatening, that is, in the opinion of the Investigator, the AE places the patient at immediate risk of death from the event as it occurred; it does not include a reaction that, had it occurred in a more severe form, might have caused death.
- Requires inpatient hospitalization or prolongation of an existing hospitalization that occurs during the course of a patient's participation in a clinical study, except for those due to the following:
  - A surgery or procedure that was planned before the patient entered the study and which is part of the planned study procedure.
  - Nonmedical reasons (eg, elective hospitalization for social reasons or due to long travel distances or for prophylactic patient observation), in the absence of an AE.

Note: "Inpatient hospitalization" means the patient has been admitted to a hospital for medical reasons.

- Results in persistent or significant disability or incapacity.
- Is a congenital anomaly or birth defect.
- Is an important medical event that, based upon appropriate medical judgment, may jeopardize the patient and may require medical or surgical intervention to prevent one of the other outcomes listed above (eg, a new cancer that is not a condition of the study indication or is a serious symptom of study drug overdose).

An efficacy failure is not considered an SAE. The Investigator should attempt to establish a diagnosis of the event based on signs, symptoms, and/or other clinical information. In such cases, the diagnosis will be documented as the AE and/or SAE and not the individual signs/symptoms.

## 10.7 Serious AE Reporting

Serious AEs will follow the same monitoring process as referenced in Section 10.2; however, events occurring after the patient has provided informed consent, but before the first dose of study treatment or confirmed screen failure, will be collected as medical history unless the event is either new and attributed to protocol-mandated procedures by the Investigator or there is a significant change in the rate of occurrence or an increase in the severity of the pre-existing condition which is judged to be clinically important and attributed to the protocol-mandated procedures by the Investigator. Any new or clinically significant changes in the patient's medical

and/or cancer history that occur after the first dose of drug and meet the SAE criteria will be recorded as SAEs. All SAEs meeting serious criteria, from the time of treatment randomization through 90 days after cessation of study treatment or 30 days after cessation of study treatment if the patient initiates new anticancer therapy, whichever is earlier, must be reported by the Investigator to Nektar Therapeutics Drug Safety immediately (ie, no more than 24 hours after learning of the event).

In addition, all SAEs that occur beyond 90 days after the last dose of all study drug(s) that are assessed by the Investigator as related to study drug(s) will also be reported to Nektar Therapeutics Drug Safety immediately without undue delay, under no circumstances later than 24 hours following knowledge of the event.

All AEs and SAEs will be recorded in the eCRF database within the timelines outlined in the eCRF completion guideline. At the time of study start, SAEs may be reported using a paper SAE reporting form. During the study conduct, sites may transition to an electronic SAE (eSAE) system. Nektar or designee will provide training and account information prior to implementing an eSAE system at each site.

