- d. Within 5 calendar days following randomization, the patient should receive the first dose of study treatment.
- e. Physical examinations must occur within 5 days prior to administering study drug(s). A full physical examination should be conducted during Screening; targeted physical examinations should be conducted on Day 1 of Cycles 1 and beyond and at the post-treatment follow-up visits. See Section 10.19 for additional details.
- f. See Section 10.20. Weight is to be reported at each vital sign visit, height at screening only. On dosing days, vital signs are to be taken and recorded as follows:
  - **For Arm A (bempegaldesleukin/pembrolizumab):** prior to bempegaldesleukin infusion and 30 ( $\pm$  10) minutes following the end of pembrolizumab infusion.
  - **For Arm B (pembrolizumab monotherapy):** prior to pembrolizumab infusion and 30 ( $\pm$  10) minutes following the end of pembrolizumab infusion.
- g. ECOG performance status assessments for Day 1 of each cycle must occur within 5 days prior to administering study drug(s) (see Appendix 3). If the Cycle 1 Day ECOG assessment will be performed within 7 days of the Screening assessment, the ECOG assessment will not need to be repeated.
- h. ECG must be done within 14 days of the date of randomization. See Section 10.21.
- i. A standard echocardiogram or MUGA must be performed for all patients within 60 days prior to randomization to assess for cardiac function and left ventricular ejection fraction (LVEF). See Section 10.22.
- j. Pregnancy test information is provided in Section 10.16.1. Women of childbearing potential (WOCBP) must have a screening negative serum or urine pregnancy test within 28 days prior to randomization. A negative highly sensitive pregnancy test (urine or serum as required by local regulations) is required within 24 hours for urine or within 72 hours for serum before the first dose of study treatment.
- k. Screening hematology and chemistry and coagulation must be drawn within 10 days of the date of randomization. Hematology and chemistry assessments for Day 1 of each cycle must be drawn within 5 days prior to administering study drug(s). See Section 10.18 and Appendix 1.

- l. See [Appendix 1](#). Screening thyroid function tests must be drawn within 28 days of the date of randomization. Thyroid function tests may be obtained within 5 days of administration of study drugs.

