### 6.7.2.2 Blood Pressure Medications for Patients Receiving Bempegaldesleukin

For patients in Arm A receiving bempegaldesleukin:

- Consideration should be given to withholding antihypertensive medications including diuretics, as well as other drugs with hypotensive properties (eg, alpha blockers for benign prostatic hyperplasia), particularly when therapy involves multiple antihypertensive drugs and classes other than thiazide diuretics. If withholding antihypertensive medications, withhold no less than 12 hours and no more than 48 hours prior to each dose of bempegaldesleukin.
- Patients who are receiving medications with antihypertensive effects for the treatment of coronary artery disease (eg,  $\beta$ -blockers, calcium channel blockers, nitrates, etc.) should be able to withhold these drugs prior to initiation of treatment at the Investigator's discretion.
- Antihypertensive medications may be reinstated in between doses of bempegaldesleukin at any time as clinically indicated (eg, based on blood pressure monitoring results).
- For patients receiving  $\beta$ -blockers, consider a step-wise tapering of doses before initiation of bempegaldesleukin to avoid reflex tachycardia. If Grade  $\geq 2$  hypertension is observed in any cycle, patients should be monitored more frequently (at least weekly) until a new stable antihypertensive regimen is identified. Patients may be monitored more frequently at the discretion of the Investigator as clinically warranted.

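### Section 10.7, Table 11 and Sections 10.2 and 10.5 give two start points for SAE reporting, so a serious event between randomization and first dose falls under incompatible rules

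*Protocol*

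**What the plan says.** Two start points appear in the Protocol.

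**Randomization.** The third sentence of Section 10.7 covers "All SAEs meeting serious criteria, from the time of treatment randomization through 90 days after cessation of study treatment" and requires the report within 24 hours of the site learning of the event. In Table 11 the main reporting column is headed "Randomization/ Allocation through Protocol-specified Follow-up Period". Under it, all nonserious AEs, SAEs and AESIs are to be reported.

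**First dose.** Section 10.7 opens by applying the Section 10.2 process to SAEs. It then says that events after consent "but before the first dose of study treatment or confirmed screen failure, will be collected as medical history", with an exception for events the Investigator attributes to protocol-mandated procedures. Its second sentence covers changes in medical or cancer history "that occur after the first dose of drug and meet the SAE criteria will be recorded as SAEs". Section 10.2 starts AE reporting once the first dose has been given and has the same medical-history rule and exception. Section 10.5 starts both serious and nonserious AEs at first administration. Before that it adds only procedure-related AEs, and it does not mention medical history.

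The two start points differ in time: "Within 5 calendar days following randomization, the patient should receive the first dose of study treatment" (Table 1 footnotes; also Section 6.2.1). Section 3.2.1 states that the trial is open-label and that withholding of antihypertensives applies to Arm A only. For patients on beta-blockers in that arm, Section 6.7.2.2 asks the site to "consider a step-wise tapering of doses before initiation of bempegaldesleukin to avoid reflex tachycardia".

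**The concern.** A site cannot follow both rules for a serious event that falls after randomization and before dosing and that nobody attributes to a mandated procedure. One rule calls for a report to the sponsor within 24 hours. The other calls for a line in the medical history, where the event reads like a baseline condition.

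Three other provisions depend on the same unsettled start:

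- Section 10.6 requires events leading to death to be reported if they fall within the protocol's reporting period.
- Section 10.12 puts AESIs (cerebrovascular accident) in both arms on the SAE timeline, so that reporting does not differ between arms. For that timeline it points to both Table 11 and Section 10.7.
- The Safety population in Section 11.3 requires at least one dose or partial dose. A patient who has an event in the gap and is never dosed is outside it.

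The arm is known in the gap, and some preparation applies to Arm A only. Antihypertensives, if withheld, are stopped 12 to 48 hours before a dose, and a beta-blocker taper is to be considered before treatment starts. Both steps are left to the site's discretion, so it is unclear whether an event that follows them counts as due to a mandated procedure.

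**Working it through.** The plan gives no figure to reproduce. The check is a comparison of rules, followed by a ceiling on exposure.

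**Start of reporting, by place**

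| Place | Covers | Start |
|---|---|---|
| 10.7, sentence 1 | SAEs | First dose; earlier events to medical history unless attributed to a mandated procedure |
| 10.7, sentence 2 | Changed history meeting SAE criteria | First dose |
| 10.7, sentence 3 | All SAEs, 24-hour report | Randomization |
| Table 11 | Nonserious AEs, SAEs, AESIs | Randomization |
| 10.2 | AEs (10.7 applies it to SAEs) | First dose; same medical-history rule |
| 10.5 | Serious and nonserious AEs | First dose, plus earlier procedure-related AEs |

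**Test case.** A patient is randomized on day 0, has a serious event on day 2 and is due for dosing on day 4. If the Investigator attributes the event to a mandated procedure, every rule treats it as reportable. If not, 10.7 sentence 3 and Table 11 require an SAE report, while 10.7 sentence 1 and 10.2 require a medical-history entry. The conflict is confined to this second branch.

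**Ceiling on exposure.** Inputs: about 500 patients, 250 per arm (Synopsis), and 5 days for everyone.

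- All patients: 500 × 5 = 2,500 patient-days; 2,500 / 365.25 = 6.8 patient-years.
- Arm A, full gap: 250 × 5 = 1,250 patient-days = 3.4 patient-years.
- Arm A, 48-hour withholding only: 250 × 2 = 500 patient-days = 1.4 patient-years, even if every Arm A patient took antihypertensives.

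Table 1 places randomization in the Day 1 column, so many gaps may be shorter. The 5 days is worded as an expectation, so a few could be longer.

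**Events.** The documents give no SAE rate for this interval. With an assumed 0.5 to 1.5 SAEs per patient-year, 6.8 patient-years would hold 3.4 to 10.3 SAEs, and the 1.4 patient-years of withholding would hold 0.7 to 2.1. These figures only restate the assumed rates at maximum exposure.

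**Deaths, for scale.** The planning median OS in the pembrolizumab arm is 12.3 months (Section 11.2.2), or 12.3 × 365.25 / 12 = 374.4 days. With a constant hazard applied to all patients, P(death by day 5) = 1 − exp(−ln 2 × 5 / 374.4) = 0.92%, or 500 × 0.0092 = 4.6 deaths. This is likely too high for SAE purposes: exclusion criterion 4 removes patients with a life expectancy under 3 months, and Section 10.9 keeps deaths due solely to the disease out of SAE reporting.

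**The case against.** The strongest defence is that the operative rules already favour randomization. The only sentence in Section 10.7 that says what must go to the sponsor within 24 hours starts there, Section 10.5 refers to Table 11 for time frames, and Table 11 has its own AESI row requiring all such events. A careful site would report. This lowers the chance of error but does not remove the conflict, because the medical-history rule opens the same section and is repeated in Section 10.2.

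Four stronger readings are tempting, and the documents do not support them:

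- **That the safety comparison is biased.** The endpoint in Section 4.2 rests on treatment-emergent AEs and SAEs, and safety is summarized in dosed patients. If treatment-emergent qualifies both terms, events before the first dose are outside the comparison under either rule. The grammar leaves a little doubt, so the accurate statement is that the comparison is probably unaffected.
- **That events are lost.** Under the narrower rule they are still recorded, as medical history. Classification and speed of reporting change.
- **That under-reporting in Arm A is shown.** It is an inference from discretionary steps. The withholding window is written into the protocol, and an Investigator might well attribute a resulting event to the protocol and so keep it as an SAE. Nor can these be hypotensive effects of bempegaldesleukin, since none has been given.
- **That a definite number of SAEs is affected.** Any count rests on rates not in the documents.

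**Conclusion.** The contradiction stands, within Section 10.7 and between Table 11 and Sections 10.2 and 10.5. It concerns serious events between randomization and first dose that are not attributed to a mandated procedure. It could include events after the Arm A-only blood-pressure medication steps, subject to the Investigator's attribution. Table 11 extends the same conflict to nonserious AEs and AESIs.

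The size is small: about 6.8 patient-years if all 500 patients use the full 5 days, with an event count that cannot be derived. OS is untouched, because deaths count from randomization in all randomized patients. What changes is whether a site owes a 24-hour report.

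The SAP records that the trial was discontinued with one patient enrolled and treated, and it plans listings only, so the effect on the final data is minimal. The point is about the protocol as written. It is worth correcting because the instruction is inconsistent, not merely incomplete, and the correction is nearly free.

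**What to change.** Reconcile Sections 10.2, 10.5 and 10.7 with Table 11:

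1. Report SAEs, AEs and AESIs from randomization in both arms.
2. Limit the medical-history rule, with its exception for mandated procedures, to the period from consent to randomization.
3. List SAEs between randomization and first dose by randomized arm for all randomized patients, including any never dosed.
4. Leave the treatment-emergent definition at first dose, so that the planned safety summaries do not change.

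The cost is wording in three sections and one listing. The downside is a few more SAE reports, some unrelated to drug. No dose, clinical rule or efficacy analysis is affected.
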